#### 9.3 POPULATIONS FOR ANALYSES

Prior to studying the NDURE intervention in a phase II clinical trial, we will pre-test our intervention in n=3 patients to ensure proper implementation into clinical workflow. These patients will participate in the intervention and outcome assessment only for the purposes of pre-testing and assessing our implementation into clinical workflow but not for the purposes of analysis towards any of the study endpoints.

For the efficacy analysis, we will utilize a modified intention-to-treat (ITT) population. Participants will be part of the modified ITT population as defined by the following criteria:

- 1. Randomized to NDURE or Usual Care
- 2. Receipt of curative intent surgery at MUSC
- 3. Indication for PORT (with or without concurrent chemotherapy) per NCCN Guidelines based on the presence of at least one of the following adverse features on final pathologic evaluation: ENE, positive margin, pT3 or pT4 primary, N2 or N3 nodal disease, nodal disease in levels IV or V, PNI or LVI

As such, the modified ITT analytic population addresses the fact that eligibility, registration, randomization, and delivery of a portion of the intervention (NDURE or Usual Care) occur prior to definitive treatment of the HNSCC. However, the primary study objective (and endpoint) are defined and evaluable only for patients who undergo surgery for HNSCC and have an indication for adjuvant therapy (which can only be definitively known following surgical resection). As such, we expect that a predictable subset of patients will be enrolled in the study, based on meeting all inclusion, be randomized to NDURE or Usual Care, receive a portion of the intervention (NDURE Visit 1) and then subsequently develop a study exclusion criterion based on interval information that becomes available later in the clinical course that cannot be known at the time of study enrollment and registration, namely:

- failure to undergo curative intent surgery at MUSC (exclusion criteria #4)
- lack of indication for PORT (with or without chemotherapy) per NCCN Guidelines (exclusion criteria #5)

As such, patients who meet study inclusion criteria but subsequently develop exclusion criteria #4 or #5 during the course of the study will be replaced since the primary endpoint is anchored to findings that occur after analysis of the pathologic specimen obtained during surgery. Patients in the modified ITT population for whom the primary endpoint is not evaluable due to loss to follow-up will be considered navigation failures, and their time to PORT will be treated as exceeding 6 weeks for the purposes of analysis.

We will also perform an efficacy analysis on the per-protocol analytic dataset, a subset of the modified ITT population who completed all 3 NDURE study sessions. These patients are judged to have complied with the protocol sufficiently to ensure that these data would be likely to represent the effects of the NDURE intervention according to the underlying scientific model.

# 9.4 STATISTICAL ANALYSES

# 9.4.1 GENERAL APPROACH

We will construct graphical displays and calculate descriptive statistics (e.g. frequencies and percent for categorical variables, and mean, median, standard deviation, and range for continuous variables). Covariates will be specified below. For inferential tests, we will use a p-value of 0.05, two-sided, and 95% confidence intervals (CIs) to assess statistical significance (Type I error). Normality of the data will be assessed before underlying statistical procedures will be performed. We will evaluate variable transformations as needed to satisfy assumptions and consider transformations of variables to induce approximate normality and stabilize variance as needed. Nonparametric tests will be applied when appropriate.

9.4.2 ANALYSIS OF THE PRIMARY ENDPOINT(S)

For the primary endpoint, delays starting PORT, the proportion of patients who start PORT more than 6 weeks after surgery and corresponding 95% CI will be calculated for the overall cohort and for white and AA subgroups separately. We will calculate racial disparities in PORT delay by comparing the difference in the rate of PORT delay (more than 6 weeks after surgery) between white and AA patients.

# 9.4.3 ANALYSIS OF THE SECONDARY ENDPOINT(S)

We will analyze time-to-PORT as a continuous variable and estimate median time-to-PORT for the cohort overall and for AA and white subgroups using Kaplan-Meier curves with Greenwood variance estimation for the corresponding 95% Cls. We will calculate racial disparities in time-to-PORT by comparing the difference in median time-to-PORT between white and AA patients.

We will compare the findings from our phase II trial of NDURE (rate of PORT delay; median time-to-PORT for the cohort overall and for racial disparities in each endpoint) to historical controls (at MUSC and nationally) using Fisher's exact test. If the upper bound of the 95% CI for the rate of delayed PORT (and racial disparities in delayed PORT) is at or below the lower bound of the 95% CI for the similar endpoint in our historical controls, we can conclude that the preliminary estimates of the therapeutic activity of NDURE (i.e. clinical benefit) suggest that further rigorous testing of the efficacy of the PN intervention in a larger clinical trial is warranted based on these phase II results. We will nevertheless interpret findings relative to historical control cautiously given that the data do not arise from a randomized trial.

For the secondary endpoints of barrier reduction and unresolved barriers, we will calculate the proportion of unresolved barriers and the frequency of unresolved barriers (respectively) at the end of NDURE, consistent with prior PN studies. We will use logistic regression to assess the relationship between unresolved barriers and the rate of PORT delay (primary endpoint), controlling for covariates listed in **Section 8.1**.

Secondary endpoints for feasibility, acceptability, fidelity and HNC care delivery will be analyzed as follows. For study accrual, we will calculate the proportion and frequency of eligible patients who accrue (overall, white, and AA). Given its pilot nature, the study is not designed to evaluate racial differences in accrual, although reasons for study decline will be collected, analyzed by race, and used to refine recruitment. NDURE completion will be analyzed as 1) the percentage of enrolled patients who attend all three in-person NDURE sessions and 2) the proportion of three in-person NDURE sessions that are completed. For navigator caseload, we will consider the frequency of simultaneous cases navigated. Navigator time allocation for direct and indirect time, as well as patient-report measures of satisfaction with navigation (acceptability) will be summarized as described above for continuous data. NDURE fidelity will be analyzed as the proportion of enrolled patients who have a BRP documented in the EMR. For HNC care delivery processes, we will calculate the proportion of patients receiving each key HNC care delivery process.

For secondary endpoints evaluating the theoretical constructs underlying NDURE (care coordination, support, perceived susceptibility, severity, barriers, and self-efficacy), we will estimate the mean change in each measure (pre-post) as well as standard deviations and 95% CIs for each; comparisons will be conducted using Wilcoxon sign-rank test. Baseline levels of each dependent variable will be controlled in each model; additional covariates will be considered by examining associations between potential covariates and each dependent variable using linear regression (p < .10 where the change in each outcome measure is the dependent variable). This method will allow estimation of intervention effects while adjusting for potential confounders.

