#### **1 PROTOCOL SUMMARY**

#### 1.1 SYNOPSIS

- Title:Single-arm, Phase II Study Evaluating the Clinical Impact of Navigation
on Delays and Racial Disparities Starting Postoperative Radiation
Therapy for Adults with Locally Advanced Head and Neck Cancer: The
NDURE Study
- Grant Number: 2K12CA157688-6
- Study Description: In this study, we evaluate the feasibility, acceptability, preliminary clinical impact, and preliminary behavioral impact of NDURE (Navigation for Disparities and Untimely Radiation thErapy), our multi-level, theory-based navigation intervention to improve timely, equitable post-operative radiation treatment (PORT) among Head and Neck Cancer (HNC) patients. We hypothesize that NDURE will be feasible, acceptable, improve the timeliness of PORT for white and African American (AA) HNC patients and decrease disparities in delay between the two groups by improving system-, interpersonal-, and individual-level health behavior constructs.

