#### 2 INTRODUCTION

#### 2.1 STUDY RATIONALE

HNC is responsible for 14,000 deaths annually in the US and has poor survival (50% at 5 years) despite intense treatment including surgery, radiation, and chemotherapy. HNC is also a disease with significant racial disparities in mortality; AAs have a 51% relative decrease in survival compared to whites. Delays starting PORT after HNC surgery are a key driver of high mortality for all HNC patients and racial disparities in survival for AAs. As such, the delivery of timely PORT is an appealing therapeutic target to address both issues. We have shown that delayed, non-guideline-adherent PORT initiation (> 6 weeks after surgery) affects 56% of HNC patients, is 31% more common in AA HNC patients than whites, is associated with an 11% absolute decrease in 5-year survival, and is a key driver of racial differences in mortality. Our pilot qualitative data suggest that treatment toxicity, travel distance, care coordination, finances, support, knowledge, and communication are barriers to timely, equitable PORT. Delivering timely PORT to all HNC patients is critical to prevent excess mortality and racial disparities in survival. Unfortunately, effective interventions to decrease delays and racial disparities starting PORT are unknown, due in part to the lack of understanding of the relevant barriers in this clinical setting. One potential strategy to improve timely, equitable PORT is patient navigation (PN), a barrier-focused intervention that improves the timeliness and racial equity of initial cancer care (screening, treatment initiation). However, the impact of PN on delays and racial disparities starting PORT, a different point on the cancer care continuum than screening and treatment initiation, is unknown. In this proposal, we extend our work to develop and evaluate the

feasibility, acceptability, and preliminary clinical impact of NDURE, our multi-level, theory-based PN intervention to improve timely, equitable PORT among HNC patients.

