# 4 STUDY DESIGN

### 4.1 OVERALL DESIGN

We will conduct a single-site, single-arm phase II clinical trial of NDURE among HNC patients undergoing surgery and PORT (n=45; AA n=15; white n=30). NDURE is a theory-based, multi-level PN intervention consisting of three in-person, clinic-based sessions of manualized PN with multiple intervention components that target system- (care coordination), interpersonal- (social support), and individual- (HBM; perceived susceptibility, severity, barriers, self-efficacy) level health behavior theoretical constructs to reduce barriers to care, increase HNC care delivery, and improve clinical outcomes (timely, equitable PORT). NDURE will be delivered from surgical consultation to PORT initiation (~3 months). The three in-person NDURE navigation sessions, which are expected to take 30-60 minutes each, will coincide with the presurgical consult, hospital discharge, and 1st postoperative clinic visit, time points chosen to facilitate case identification and coordination across key care transitions. Measures of PORT delay will be analyzed overall (primary outcome) and for racial differences (secondary outcome). Measures of the preliminary clinical impact of NDURE on PORT barrier reduction and delivery of key HNC care processes will be collected (secondary outcome), feasibility (secondary outcome; accrual rate, NDURE completion rate, PN caseload), acceptability (secondary outcome; satisfaction with PN). Measures of the theoretical constructs underlying the multi-level, theory-based NDURE intervention will be compared pre- and post-intervention. Post-intervention qualitative work with patients and providers will help refine NDURE.

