#### Secondary Endpoints Clinical Outcomes

Racial disparities in initiation of PORT > 6 weeks after surgery is defined as the difference in the rate of initiation of PORT > 6 weeks after surgery between white and AA HNC patients.

Days between surgery and the start of PORT is defined as the time, in days, between the date of definitive surgical resection to the initiation of radiation therapy. All of the criteria used to adjudicate the date of the definitive surgical procedure described for the primary outcome measure will be applied to this measure.

Barriers resolved is the number of barriers identified by the navigator that are resolved during the NDURE intervention, as determined by the navigator log.

Unresolved barriers is the number of barriers identified by the navigator that are not resolved during the NDURE intervention, as determined by the navigator log.

Pre-Surgical Radiation Consultation is defined as the attendance by the patient at a consultation with a radiation oncologist (at MUSC or elsewhere) prior to surgery to discuss RT in the definitive or adjuvant setting

Pre-Radiation Therapy Dental Extractions is defined as the extraction of teeth prior to discharge from the index hospitalization for the definitive surgical procedure. Patients who are edentulous are not evaluable for this measure.

Surgery to Pathology Report </= 7 days is defined as the production of the pathology report from the definitive surgical procedure within the EMR within 7 calendar days of the definitive surgical procedure. Addenda to the pathology report at the request of the HNC team (e.g. tumor p16 status) are not counted in this measure.

Surgery to PORT Referral </= 10 days is defined as the placement of a referral for PORT, at MUSC or elsewhere, within 10 calendar days of the definitive surgical procedure.

RT Referral to Consult </= 10 days is defined as the evaluation of the patient at a postoperative consultation with a radiation oncologist within 10 calendar days of the referral being placed (or postoperative appointment being scheduled in cases in which care has been established and the return visit is no longer a consultation). The consultation may occur in the clinic or the hospital depending upon clinical circumstances.

RT Consult to Initiation </= 21 days is defined as the initiation of PORT within 21 calendar days of the patient being evaluated by a radiation oncologist for PORT.

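### The go rule treats the racial gap in delay like a delay rate: with no stated sign and no zero target, it can credit a reversed or a widened gap as benefit

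*Combined protocol and SAP*

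**What the plan says.** The Synopsis (1.1) states the aim as to "decrease disparities in delay between the two groups", and the effect on racial disparities is the first secondary objective. Section 8.1 says the disparity "is defined as the difference in the rate of initiation of PORT > 6 weeks after surgery between white and AA HNC patients". Section 9.4.2 obtains it by "comparing the difference in the rate of PORT delay (more than 6 weeks after surgery) between white and AA patients". Neither passage says which rate is subtracted from which, whether the absolute value is meant, or that zero is the goal.

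Section 9.4.3 then sets one decision rule for two quantities. It reads "If the upper bound of the 95% CI for the rate of delayed PORT (and racial disparities in delayed PORT) is at or below", and what follows is "the lower bound of the 95% CI for the similar endpoint in our historical controls". Meeting the rule lets the investigators conclude that a larger efficacy trial is warranted. The historical controls are MUSC 2014-2016 and the National Cancer Database 2006-2014. The documents give no confidence interval for the disparity in either.

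**The concern.** An upper bound at or below a historical lower bound is a sensible signal for a quantity where less is always better. A signed difference between two groups is not such a quantity. Moving down from a positive gap is good until zero is reached; beyond zero, the inequality grows again in the other direction. The rule does not stop at zero. If the difference is taken in the order in which the groups are named, the historical value is negative and moving down means a worse gap for AA patients.

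At stake is the conclusion on the first secondary objective. With the sign left open, a result that moves away from equity could be reported as meeting the rule, and the direction could be chosen after the data are seen.

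**Working it through.** **Inputs.** Planned numbers are "n=45; AA n=15; white n=30" (Section 4.1), with two-sided 95% intervals (Section 9.4.1). Nationally, delay "affects 56% of HNC patients" (Section 2.1) and is 31% more common in AA patients (Sections 2.1 and 2.2). The AA share of 22% is the MUSC figure from Section 5.5; applying it to the national data is an assumption. Section 9.4.3 does not name an interval method for the difference, so Wald and Newcombe (Wilson-based) intervals are both used.

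**The plan's own precision figures.** 1.96 × √(0.25/n) gives 0.146 for n=45 and 0.253 for n=15. These match the 0.15 and 0.25 in Section 9.2. Section 9.2 gives no figure for the difference between the races.

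**Precision of the difference.** With a common rate p, the half-width is 1.96 × √(p(1-p)(1/15 + 1/30)). This is 0.310 at p=0.5 and 0.248 at p=0.2.

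**Reading 1, AA minus white.** Take AA 2/15 (13%) and white 15/30 (50%), a gap of -0.367.
- Wald: standard error √(0.1333×0.8667/15 + 0.25/30) = 0.1266; upper bound -0.367 + 1.96×0.1266 = -0.12.
- Newcombe: Wilson upper limit for 2/15 is 0.379 and lower limit for 15/30 is 0.332; upper bound -0.367 + √((0.379-0.133)² + (0.500-0.332)²) = -0.07.

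Both lie below any historical bound of zero or above. The disparity part of the rule is met by a 37-point gap against white patients.

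**Reading 2, white minus AA.** AA patients were delayed more often historically, so the historical gap and its lower bound are negative. To pass, the NDURE upper bound must lie at or below that lower bound. The NDURE estimate must then be more negative than the historical one, which is a wider gap against AA patients. Example: white 6/30 and AA 12/15, difference -0.60. The Wald upper bound is -0.60 + 1.96×√(0.16/30 + 0.16/15) = -0.35 (Newcombe -0.29), which passes historical bounds down to about -0.35. Equal observed rates, other than 0% or 100%, have an upper bound above zero and fail.

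**Reading 3, absolute difference.** A large reversed gap would fail, as it should. The plan does not state this reading.

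**Assumed historical bound for Reading 1.**
- If 31% is a risk ratio: white = 0.56/(0.78 + 0.22×1.31) = 0.524, AA = 0.687, gap 0.16.
- If it is an odds ratio: white 0.546, AA 0.611, gap 0.07.

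Using these point estimates as the lower bound favours the rule, since a true lower bound lies below its estimate. For MUSC the bound is unknown.

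**Equality under Reading 1.** Equal observed rates from 13% to 87% give Wald upper bounds of 0.21 to 0.31 and Newcombe bounds of 0.19 to 0.29. All exceed 0.16 and fail.

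**Chance of passing under Reading 1** (exact binomial enumeration, Wald, bound 0.07 to 0.16):

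| True delay rates | Chance of passing |
|---|---|
| Both 50% | 9-18% |
| Both 20% | 13-32% |
| AA 30%, white 50% | 48-66% |

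Newcombe gives 7-20% for the first row and 41-65% for the last.

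**The case against.** The strongest reply is that the intended direction is clear from context. Delay is described throughout as more common in AA patients and the aim is to reduce the disparity, so no analyst following this protocol would score a wider gap against AA patients as success. That is fair as to intent, and it makes Reading 2 unlikely in practice. It does not help Reading 1, which is the natural one and still rewards reversal.

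A reader might infer that the missing sign and zero are why equality fails, or that the rule can never recognise equity. The documents do not support this. Under AA minus white, a precise estimate of zero would pass any positive historical lower bound. Equality fails here because 15 and 30 patients give a wide interval, and for MUSC even that cannot be shown without the historical bound. Nor does every reversal pass: at a bound of 0.15, the observed reversal must be roughly 13 to 20 points, for white rates of 20-60%.

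It can also be said that the rule may require the overall rate to pass as well. That limits how far white patients could worsen, but it does not remove the defect. In the Reading 1 example the overall rate is 17/45 = 0.378, with upper bound 0.378 + 1.96×√(0.378×0.622/45) = 0.52, which clears an assumed historical lower bound of 0.55. The Reading 2 example gives 18/45 = 0.40 and 0.54, which also clears it. The Reading 1 example is not evidence of harm, since both races fall below the rates derived above; the error is in calling a 37-point reversed gap a reduced disparity.

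Finally, Section 9.4.2 reports each race's rate with its interval, so a reversal would be visible, and the plan calls itself an unpowered pilot whose historical comparisons need caution. This limits the consequence. The stated caution concerns the lack of randomisation, though, not a rule pointing the wrong way.

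**Conclusion.** Wrong as written, and worth correcting before results are seen. The central defect follows from the text alone: a rule for a quantity that should be as low as possible is applied to one that should be zero. Under AA minus white it credits a large reversal; under white minus AA it can credit only a widened gap. Neither conclusion needs a historical figure beyond the direction of the historical gap.

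The size under AA minus white rests on assumptions: a historical lower bound of 0.07 to 0.16 taken from the national figures, and the planned 15 and 30 patients. On those terms, a true 20-point reversal (30% against 50%) passes 48-66% of the time, and true equality at 50% passes 9-18%. The low figure for equality reflects interval width and should be reported separately from the sign problem.

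**What to change.** 1. In Sections 8.1, 9.4.2 and 9.4.3, define the disparity as the AA delay rate minus the white delay rate, and state that zero is the target.
2. In Section 9.4.3, delete the parenthesis that brings racial disparities into the go rule, so that the rule applies to the delay rate only.
3. Report the AA-minus-white gap, and its change from the historical gap, with 95% CIs beside each race's own delay rate, without a pass/fail rule on the gap. With half-widths of 0.25 to 0.31 at rates of 20-50%, a threshold on the gap would mostly reflect noise.

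The cost is a wording change, with no new trial data. The change from the historical gap needs that gap and its CI, which Section 9.4.3 already presupposes but the documents do not give. The downside is that the first secondary objective becomes descriptive, which is consistent with the pilot status in Sections 4.2 and 9.1.

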Sites/Facilities Enrolling	Hollings Cancer Center (HCC) Head and Neck Tumor Center. The Head			
Darticipante:	and Neck Tumor Conter is a high volume, multidisciplinary conter			
	designed for unsurpassed clinical care and entimized for integration of			
	response not unsurpassed chilical care and optimized for integration of			
	research activities. The mead and Neck Tumor Center IS a regional			

Description of Study Intervention/Experimental Manipulation: NDURE is a theory-based, multi-level patient navigation (PN) intervention consisting of three in-person, clinic-based sessions of manualized PN with multiple intervention components that target system- (care coordination), interpersonal- (social support), and individual- (health belief model (HBM); perceived susceptibility, severity, barriers, self-efficacy) level health behavior theoretical constructs to reduce barriers to care, increase HNC care delivery, and improve clinical outcomes (timely, equitable PORT). NDURE will be delivered from surgical consultation to PORT initiation (~3 months). The three in-person NDURE navigation sessions, which are expected to take 30-60 minutes each, will coincide with the presurgical consult, hospital discharge, and 1st postoperative clinic visit, time points chosen to facilitate case identification and coordination across key care transitions.

Study Duration: 18 months

Participant Duration: 5 months

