# 6 STUDY INTERVENTION(S) OR EXPERIMENTAL MANIPULATION(S)

#### 6.1 STUDY INTERVENTION(S) OR EXPERIMENTAL MANIPULATION(S) ADMINISTRATION

#### 6.1.1 STUDY INTERVENTION OR EXPERIMENTAL MANIPULATION DESCRIPTION

NDURE is a theory-based, multi-level PN intervention consisting of three in-person, clinic-based sessions of manualized PN with multiple intervention components that target system- (care coordination), interpersonal- (social support), and individual- (HBM; perceived susceptibility, severity, barriers, self-efficacy) level health behavior theoretical constructs to reduce barriers to care, increase HNC care delivery, and improve clinical outcomes (timely, equitable PORT). The NDURE intervention components and targeted theoretical constructs are outlined in Table 1. NDURE will be delivered from surgical consultation to PORT initiation (~3 months). The three in-person NDURE navigation sessions, which are expected to take 30-60 minutes each, will coincide with the presurgical consult, hospital discharge, and 1st postoperative clinic visit, time points chosen to facilitate case identification and coordination across key care transitions. Contact beyond the three prescribed in-person sessions will occur with a frequency and modality (e.g. text message, email, etc.) dictated by patient and navigator need. During the first in-person session, the navigator will 1) elicit barriers and facilitators to timely PORT from the patient, caregiver, and provider, 2) develop the personalized barrier reduction plan (BRP), review it with the patient, caregiver, and provider, and 3) implement the BRP. At the two subsequent in-person sessions, the navigator will review and update the BRP in an iterative, dynamic fashion, identifying new barriers and systematically tracking resolution of prior barriers until the start of PORT. The Navigator Manual provides a structured resource to guide intervention delivery and enhance reproducibility. The Patient Guide is 1) literacy-level appropriate, 2) personalized for each patient's care pathway and BRP, 3) updated longitudinally as the patient progresses along the cancer continuum, and 4) available to patients in print and/or electronically via the patient portal in the EMR.

Table 1. NDURE Intervention Components		
Component Description Th		Theoretical Target
Clinical Tool		

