# 8 STUDY ASSESSMENTS AND PROCEDURES

#### 8.1 ENDPOINT AND OTHER NON-SAFETY ASSESSMENTS

#### Primary Endpoint

Initiation of postoperative PORT > 6 weeks after surgery is defined as more than 42 calendar days from the time of the definitive surgical resection to the initiation of radiation therapy. In situations in which the surgical management of the primary tumor and the neck are staged (i.e. occur on two different calendar days), the date of the surgery for the primary tumor will be used. In situations in which an additional surgical resection is required (e.g. re-resection of positive margins to clear residual disease), the date of the earlier (i.e. attempted definitive) surgical procedure will be used to determine the target start date for PORT.

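### The barrier-to-delay regression counts unresolved barriers at PORT start, so the exposure closes at the outcome and the association is biased toward, possibly past, the null

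*Combined protocol and SAP*

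**What the plan says.** For the barrier endpoints, Section 9.4.3 states: "we will calculate the proportion of unresolved barriers and the frequency of unresolved barriers (respectively) at the end of NDURE". The next sentence begins "We will use logistic regression to assess the relationship between unresolved barriers and the rate of PORT delay (primary endpoint" and then adds adjustment for the Section 8.1 covariates. It gives no separate time point for the exposure.

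Section 8.1 allows no other timing. It says that the unresolved-barriers endpoint "is the number of barriers identified by the navigator that are not resolved during the NDURE intervention, as determined by the navigator log". The end of the intervention is PORT start: the Synopsis and Sections 4.1 and 6.1.1 have NDURE running from the surgical consultation to PORT initiation, and Section 6.1.1 has the navigator "identifying new barriers and systematically tracking resolution of prior barriers until the start of PORT".

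Delay, the primary endpoint in Section 8.1, "is defined as more than 42 calendar days from the time of the definitive surgical resection to the initiation of radiation therapy". Section 9.3 adds that modified ITT patients whose primary endpoint cannot be evaluated because of loss to follow-up "will be considered navigation failures, and their time to PORT will be treated as exceeding 6 weeks for the purposes of analysis".

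Two further places bear on the remedy. The Flow Diagram table in Section 1 schedules Unresolved Barriers at Visits 2 to 5. Section 6.2.1 lists the content of the navigator's log: encounters, time, barriers by number and type, and actions with their outcomes. It names no resolution date.

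**The concern.** The model asks whether leaving barriers unresolved goes with late PORT, but it measures the exposure at the moment the outcome becomes known. Two consequences follow.

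- The observation window depends on the outcome. Among patients who start PORT, it covers at most 42 postoperative days for timely patients and more than 42 for delayed ones, so delayed patients have longer to get any barrier closed.
- The barriers of most interest can drop out. One that kept a patient from starting until after day 42, and was then cleared, is no longer unresolved when it is counted.

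This is the only planned analysis that links unresolved barriers to the primary endpoint, in a trial of a barrier-reduction intervention. A weak or inverse odds ratio could be read as evidence that open barriers do not matter for delay, when it partly reflects when the count was taken. A larger sample would not remove the bias.

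**Working it through.** **1. The plan's own figures.** The documents give no power, effect size or expected odds ratio for this model. Their sample-size figure is the margin of error for the delay rate: 1.96 × √(0.25/45) = 0.146, stated as 0.15. It reproduces, but it does not bear on this point.

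**2. Two illustrative patients.**

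- Patient A has a transport barrier open on day 42. It is resolved on day 60 and PORT starts on day 65. Score: delayed, 0 unresolved.
- Patient B starts PORT on day 35 with a minor barrier still open. Score: timely, 1 unresolved.

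With the count taken before day 42, patient A has at least one open barrier.

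**3. Window length alone.** Take a barrier that has no influence on PORT and an assumed exponential resolution time with mean 40 days from surgery. The chance that it is still open at PORT start is exp(−t/40).

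- Start on day 35: exp(−35/40) = 0.42.
- Start on day 65: exp(−65/40) = 0.20.

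An irrelevant barrier is thus about half as likely to count against the delayed patient (0.20/0.42 = 0.47).

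**4. Simulation.** All rates are assumptions, since the documents give none. Each scenario has 200,000 simulated patients and an unadjusted logistic regression of delay (more than 42 days) on the unresolved count.

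*Set 1.* About 3 barriers per patient; 30 to 80% must clear before PORT (blocking); mean resolution 15 or 25 days from surgery; PORT 14 days after the last blocking barrier clears, otherwise around day 30.

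- Every blocking barrier logged as resolved: odds ratio (OR) 0.24 to 0.32 at PORT start; 2.6 to 10.5 at day 21 (or at PORT start if earlier).
- 25% of blocking barriers worked around but still logged as open: 0.80 to 1.45 at PORT start.
- 50% still logged as open: 1.15 to 1.69.
- 10% still logged as open, with 80% of barriers blocking: 1.08 to 1.22.

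*Set 2.* Poisson(1.5) blocking and Poisson(1.5) non-blocking barriers; mean resolution 25 and 40 days; unhindered start about day 35 (SD 5); PORT at least 7 days after the last blocking barrier clears.

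| Scenario | OR at PORT start | OR at day 28 |
|---|---|---|
| Base case | 0.54 | 2.60 |
| 10% / 25% / 50% of blocking barriers left open in log | 0.75 / 0.96 / 1.20 | 2.60 / 2.60 / 2.60 |
| Between-patient spread in resolution speed, log SD 0.5 / 1.0 | 0.69 / 0.92 | 2.84 / 3.17 |
| Non-starters, 5% / 10% of patients with a blocking barrier | 0.66 / 0.76 | 2.48 / 2.37 |
| New barriers, 0.005 / 0.01 per day | 0.75 / 0.78 | 2.60 / 2.60 |
| Spread 0.5, 10% open, 5% non-starters | 0.97 | 2.67 |
| Spread 0.5, 25% open, 10% non-starters | 1.23 | 2.54 |

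The PORT-start odds ratio is below 1 in 10 of the 12 scenarios. In the other two it keeps about a fifth of the landmark log odds ratio: ln 1.20/ln 2.60 = 0.19 and ln 1.23/ln 2.54 = 0.22.

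*Set 3.* Further runs gave 0.26 to 1.72 at PORT start and 2.1 to 9.5 at the landmark. The PORT-start value was the lower one in every scenario. It was reversed throughout only when every blocking barrier was logged as resolved before PORT.

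Rounded over all sets: about 0.25 to 1.7 at PORT start, about 2 to 10 at a landmark before day 42. Sets 1 and 2 took the landmark count in all simulated patients, not only those yet to start PORT, so they show the scale of the contrast rather than the exact odds ratio under the fix.

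**The case against.** A reader might infer that any barrier that blocked PORT must be resolved once PORT begins, so that the association is bound to vanish or reverse. The documents do not support that. They contain no rule that PORT waits for a barrier to be logged as resolved, and no rule for when a barrier counts as resolved. Section 2.1 names barriers such as travel distance, finances, support, knowledge and treatment toxicity; several could slow PORT and still be open when it starts. The odds ratios of 0.24 to 0.32 come from assuming that every blocking barrier is cleared first. Once some stay open in the log, the odds ratio can exceed 1. This part of the objection stands.

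Loss to follow-up works the other way. Such patients are classed as delayed and may carry open barriers, which pushes the odds ratio up. This also stands, but it does not rescue the estimate. Tracking stops, so barriers remain open, and delay is then assigned by rule. That is a second artefact in the opposite direction, and the two need not cancel.

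A reader might also infer that the secondary objective on barriers and care processes depends on this model, or that the model would misdirect the later cluster-randomised trial. Neither follows. That objective maps to barriers resolved, unresolved barriers and care-process measures, which Section 9.4.3 summarises descriptively. The regression carries no decision rule. The criterion for further testing is the confidence-interval comparison of delay rates with historical controls, and Section 4.1 ties refinement of NDURE to qualitative work. Likewise, a longer window can raise barriers resolved in delayed patients, but no planned analysis compares that count by delay status.

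**Conclusion.** The timing flaw is confirmed by the plan's own text: the exposure closes at PORT start, which is also the outcome event, and no landmark, fixed-day or time-dependent count is specified for the model. The estimated barrier-to-delay association is biased toward, and possibly past, the null; its direction is not guaranteed. In all the simulations the count at PORT start gave a smaller odds ratio than the count before day 42, but the size of the gap rests on assumed barrier numbers, resolution times and logging behaviour.

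The defect is confined to one secondary association model in a pilot of 45 patients. It is still worth correcting before analysis, because the result as planned would not be interpretable in either direction.

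**What to change.** In Section 9.4.3, define the exposure for the logistic model as the number of barriers open at a point before day 42, among patients who have not yet started PORT. The third navigation session (the first postoperative clinic visit) is a natural choice, using the Unresolved Barriers records from Visits 2 to 5. The text should name the visit, because the Flow Diagram does not tie the visits to sessions or to days after surgery. It should also say how patients are handled whose third session is missed or falls after day 42.

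Keep the end-of-NDURE counts of resolved and unresolved barriers as descriptive endpoints.

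Cost: with a session-based count, SAP wording only. If a stated postoperative day is preferred, a resolution date may have to be added to the navigator log, which is a data-collection change. There are two small losses: barriers first identified after the landmark do not enter the model, and any patient who starts PORT before it is excluded from the model.
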